3.1.2 Enrollment/ Randomization

Enrollment/ randomization to study treatment must occur within 8 weeks of the first day of the last cycle of chemotherapy and is described in more detail in Section 5.4. Study treatment must be initiated within 3 days of randomization.

3.1.3 Double-blind Treatment Phase

The Double-blind Treatment Phase will continue in 28-day treatment cycles. The first dose of oral study treatment will be administered on Cycle 1 Day 1 and continue BID throughout the cycle as monotherapy; IV study drug will begin on Cycle 2 Day 1 (C2D1). Details on study drug administration are described in Section 5.5. During the Double-blind Treatment Phase, patients will come into the study site for a visit on Day 1 and Day 15 of Cycles 1 and 2, and on Day 1 of every cycle thereafter. Study treatment will continue until 24 months after initiating oral/IV combination study treatment, disease progression, or unacceptable toxicity, whichever happens first.

During the Double-blind Treatment Phase (continuous 28-day treatment cycles), patients will be monitored for safety and efficacy. Assessments will include AEs, physical examination, vital signs and weight measurement, central laboratory hematology, serum chemistry, and CA-125 measurement, concomitant medications, therapies and procedures, ECOG performance status, disease status assessment, ctDNA analysis, study drug administration and accountability, and PRO. ECGs and urinalysis will be performed as clinically indicated.

Blood samples will also be collected to determine whether any mutation identified is of germline or somatic origin and for PPK analyses.

Patients will be assessed for disease status per RECIST v1.1 every 12 calendar weeks (flexibility with scheduling within 1 week prior to planned imaging date is permitted) relative to C2D1 (the first scan will be 16 weeks after initiation of oral study treatment) for the first 3 years and every 24 weeks thereafter until objective radiological disease progression; disease status will also be assessed at discontinuation of treatment and as clinically indicated. Disease progression will only be determined by RECIST v1.1 (Section 7.5.3.1). Patients with a CR at study entry will only be considered to have disease progression if a new lesion is identified based on guidelines outlined in RECIST v1.1. Patients who meet GCIG CA-125 criteria for disease progression should have a radiologic assessment and be assessed by RECIST v1.1. If the radiologic assessment does not confirm disease progression, patients should continue on treatment and be assessed by RECIST v1.1 per the protocol schedule of assessments. Patients experiencing disease progression by RECIST v1.1, as assessed by the investigator, will be discontinued from treatment and enter follow-up. If the patient has met criteria for radiologic progression by RECIST, but the patient is still receiving benefit from the study drug(s) (eg, patient has mixed radiologic response or is continuing to have symptomatic benefit), according to the investigator, then continuation of treatment will be considered for a maximum cumulative duration of 24 months after initiation of oral/IV combination study treatment (see Section 5.13). Patients will continue to have all protocol-required assessments specified in the Schedule of Assessments (Table 5).

PRO assessment will occur on Day 1 of Cycles 1 through 3, Cycle 5, then every 12 weeks (aligning with tumor assessment scans) until treatment discontinuation or until the data cut-off for the primary endpoint analysis, whichever comes first.

All CT scans (and other imaging, as appropriate) performed during the treatment period and at treatment discontinuation will be collected for BICR.

Patients will be continuously monitored for safety. An IDMC with multidisciplinary representation will evaluate safety in compliance with a prospective charter.

3.1.4 End of Treatment

Upon treatment discontinuation, regardless of reason, patients will have an End-of-Treatment Visit. Assessments will include AEs, physical examination, vital signs and weight measurements, central laboratory hematology, serum chemistry, and CA-125 measurement, 12-lead ECG, ctDNA analysis, concomitant medications, therapies and procedures, ECOG performance status, disease status assessment (only if 12 weeks or more since last scan), study drug accountability, and PRO.

3.1.5 Open-label Safety Lead-in

Prior to the Double-blind Treatment Phase, a small, open-label safety cohort will be enrolled to assess the safety of the combination of rucaparib (600 mg BID) and nivolumab (480 mg IV on Day 1 of every 28-day cycle, starting with Cycle 2). The eligibility criteria and assessments for these patients will be the same as those described for patients enrolled in the

Double-blind Treatment Phase of the study. The safety cohort will consist of a minimum of 6 patients enrolled at sites from North America and/or Europe. A formal safety review will occur after the safety cohort has enrolled and patients have been treated with the combination for at least 28 days (ie, 1 cycle) and with oral study drug for 2 cycles. The review committee will include external experts and sponsor personnel (see Section 9.9). The data will also be shared with the Independent Data Monitoring Committee (IDMC; see below and Section 8.11). The protocol will be amended as appropriate to incorporate additional patient safety monitoring if new safety signals are noted at any review.

The safety cohort will not be enrolled, and the study will proceed directly to the Double-blind Treatment Phase, if, at the time that the first study sites are activated, a minimum of 6 patients have been enrolled in the ongoing Phase 1/2 study in prostate cancer patients (Study CA2099KD [NCT03338790]) with the same rucaparib + nivolumab combination regimen, and the safety evaluation of these patients shows no new safety signals.

Once the evaluation of the safety cohort is complete, the double-blind portion of the study can be opened for randomization in all regions with the exception of Japan. Prior to randomizing any patients in Japan, a safety cohort of at least 6 patients of Japanese ethnicity will be enrolled at investigational sites in Japan. This enrollment is contingent upon determination of a monotherapy rucaparib dose that is currently being evaluated in a Phase 1 dose escalation study (Study CO-338-081) ongoing in Japan. Nivolumab at a dose of 480 mg Q4W will be used in this study and is based on equivalence to the approved dose of 3 mg/kg Q2W in Japan for numerous indications, including melanoma, lung, and gastric cancers. Evaluation of the Japanese safety cohort will proceed in the same manner as the initial safety cohort. Once the evaluation of the Japanese cohort is complete, the double-blind portion of the study can be opened for randomization in Japan.

3.1.6 Post-treatment Follow-up Phase

All patients will be followed for at least 5 months after the last IV dose of study treatment. Safety Follow-up Visit 1 (SFU1) should occur 28 days (± 7 days) after last dose of study drug (oral or IV, whichever is later) or can be performed on the date of discontinuation if that date is at least 28 days from the last dose. Assessments will include AEs, physical examination, vital signs and weight measurements, central laboratory hematology, serum chemistry, and CA-125 measurement, ECG, ctDNA analysis (SFU1 only), concomitant medications, ECOG performance status, therapies and procedures, study drug accountability, and PRO. Safety Follow-up Visit 2 (SFU2) should occur approximately 5 months (± 7 days) from the last IV dose of study drug. The same assessments performed at SFU1 will be performed at SFU2; however, chemistry and hematology are only necessary if toxicities are present. If a patient remains on oral study drug after discontinuation of IV study drug, the SFU2 can be performed at the next cycle visit, provided it has been at least 5 months since the last IV dose.

Patients who discontinued treatment for reason other than disease progression or death should continue to have tumor scans performed at 12-week intervals relative to C2D1 (flexibility with scheduling within 1 week prior to planned imaging date is permitted) for the

first 3 years and every 24 weeks thereafter until objective radiological disease progression by RECIST v1.1 is documented, as assessed by the investigator.

An optional tumor biopsy will be collected from patients who experience disease progression/randomized treatment discontinuation and provide appropriate consent.

Patients will also be followed long-term for survival, subsequent treatments, and monitoring for secondary malignancy every 12 weeks (± 14 days) after SFU1 until death, loss to follow-up, withdrawal of consent, or study closure.

If a patient begins subsequent anticancer therapy, the sponsor will terminate collection of SAEs, with the exception of the AESIs of MDS and AML.

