- u = First dose of IV study drug occurs C2D1. Study treatment continues on Day 1 every 28-day cycle until 24 months after initiation of oral/IV combination study treatment, disease progression, or unacceptable toxicity, whichever happens first.

Table 5. Schedule of Assessments for All Patients (cont.)

- V = AEs, SAEs, and AESIs that occur after first administration of study drug through to 28 days after last dose of oral or IV study drug, whichever occurs later, and AEs/SAEs assessed as related to IV drug that occur up to 5 months after the last IV dose of study drug will be recorded. In addition, AEs that were related to a screening procedure will also be recorded. Section 8 includes the details of reporting AEs, SAEs, and AESIs. Ongoing SAEs, AESIs, or treatment-related Grade 3/4 AEs will be followed to resolution or stabilization. After the 28-day (oral) or 5-month (IV) windows, only SAEs considered as potentially study-drug related (including serious reports of pneumonitis or similar events, ie, interstitial lung disease, pulmonary fibrosis, acute interstitial pneumonitis, alveolitis necrotizing, alveolitis, hypersensitivity pneumonitis, and organizing pneumonia, if considered to be related to study drug), and AESIs of myelodysplastic syndrome (MDS) and acute myeloid leukemia (AML) regardless of causality, will be recorded. If a patient discontinues from treatment and begins a subsequent anticancer therapy, the sponsor will terminate collection of SAEs, with the exception of the AESIs of MDS and AML.
- w = An optional tumor biopsy may be collected from patients at time of disease progression/randomized treatment discontinuation. Additional consent is required. Refer to the central Laboratory Manual for detailed sample collection and handling instructions.
- x = All patients discontinued from treatment, regardless of reason, should be followed for subsequent treatments, secondary malignancy, and survival every 12 weeks (± 14 days) after SFU1 (28-days after the last dose of study drug) until death, loss to follow-up, withdrawal of consent from study, or closure of the study. Follow-up can be performed via the telephone. Diagnosis of any secondary malignancy requires appropriate documentation (ie, laboratory and/or pathology reports) and should be reported as specified in Section 8.7.

Table 6. Pharmacokinetic and Immunogenicity Sample Collections

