7.5.4 Safety Evaluations

7.5.4.1 Adverse Event Assessment

The investigator has the responsibility for assessing the safety of the patients and for compliance with the protocol to ensure study integrity. During the screening period, unless otherwise required by local regulations, SAEs which are related to protocol-mandated assessments will be reported. Once enrolled and study drug is administered, patients will be monitored for all AEs/SAEs/AESIs during study participation and until 28 days after the last dose of oral study drug and 5 months after the last dose of IV study drug, whichever occurs

later. After the 28-day (oral) or 5-month (IV) window, only SAEs assessed as potentially related to study drug (including serious reports of pneumonitis or similar events, ie, interstitial lung disease, pulmonary fibrosis, acute interstitial pneumonitis, alveolitis necrotizing, alveolitis, hypersensitivity pneumonitis, and organizing pneumonia, if considered to be related to study drug), and AESIs of MDS and AML irrespective of causality, need to be reported. Any ongoing SAEs, AESIs, or treatment-related Grade 3/4 AEs will be followed until resolution or stabilization or until loss to follow-up. AEs and laboratory abnormalities will be graded according to the NCI CTCAE grading system (v5.0) and recorded on the eCRF.

If a patient begins subsequent anticancer therapy, the sponsor will terminate collection of SAEs, with the exception of the AESIs of MDS and AML.

Complete details for monitoring AEs, including the definition of drug-related AEs, are provided in Section 8.

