In order to avoid vague, ambiguous, or colloquial expressions, the AE should be recorded in standard medical terminology rather than the patient's own words. Whenever possible, the investigator should combine signs and symptoms that constitute a single disease entity or syndrome into a final diagnosis, if appropriate. For example, fever, cough, and shortness of breath may be reported as pneumonia, if that is a reasonable diagnosis.

Each AE is to be evaluated for duration, severity, seriousness, and causal relationship to the investigational drug. The action taken and the outcome must also be recorded.

SAEs and AESIs that occur during the study or within 28 days after receiving the last dose of oral study drug or 5 months after receiving the last dose of IV study drug, whichever is later, whether or not related to study drug, must be reported immediately (ie, **within 24 hours** of knowledge of the event or additional information for a previously-reported event) to the sponsor/SAE designee. The contact information for reporting of SAEs/AESIs can be found on the SAE/ AESI Reporting Form.

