8.9 Potential Drug-Induced Liver Injury

Wherever possible, timely confirmation of initial liver-related laboratory abnormalities should occur prior to the reporting of a potential DILI event. All occurrences of potential DILIs, meeting the defined criteria, ⁴⁹ must be reported as SAEs (see Section 8.10 for reporting details).

Potential drug induced liver injury is defined as:

1. ALT or AST elevation $> 3 \times ULN$

AND

2. Total bilirubin > 2 × ULN, without initial findings of cholestasis (elevated serum alkaline phosphatase),

AND

3. No other immediately apparent possible causes of ALT/AST elevation and hyperbilirubinemia, including, but not limited to, viral hepatitis, pre-existing chronic or acute liver disease, or the administration of other drug(s) known to be hepatotoxic.

8.10 Regulatory Aspects of Serious Adverse Event and Adverse Events of Special Interest Reporting

All SAEs and AESIs, regardless of relationship to study drug, must be reported to the sponsor/ SAE designee within 24 hours of knowledge of the event, during the study through 28 days after receiving the last dose of oral study treatment and 5 months after receiving the last dose of IV study treatment, whichever occurs later, according to the procedures below. After the 28-day window, only SAEs considered to be potentially treatment-related (including serious reports of pneumonitis or similar events, ie, interstitial lung disease, pulmonary fibrosis, acute interstitial pneumonitis, alveolitis necrotizing, alveolitis, hypersensitivity pneumonitis, and organizing pneumonia, if considered to be related to study drug), and AESIs of MDS and AML regardless of treatment relationship, should be reported. It is important that the investigator provide an assessment of relationship of the SAE or AESI to study treatment at the time of the initial report. The Serious Adverse Event (SAE)/Adverse Events of Special Interest (AESI) Report Form must be used for reporting SAEs and AESIs. The contact information for reporting of SAEs and AESIs can be found on the SAE/ AESI Reporting Form.

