#### 11 SAFETY ANALYSIS

Safety and tolerability is one of the secondary study objectives. Overall safety and tolerability will be measured by the incidence of adverse events, serious adverse events, adverse events leading to discontinuation, deaths, specific laboratory abnormalities (worst grade) and changes from baseline.

The safety analyses will be presented for the safety population presenting the data for each treatment group separately (Arm A [rucaparib and nivolumab], Arm B [rucaparib], Arm C [nivolumab], and Arm D [placebo]). The analyses will be presented by the actual treatment given. Patients randomized to either treatment group containing IV Nivolumab (ie, Arm A or Arm C) who never receive Nivolumab, will be analyzed in the analogous treatment group containing IV Placebo (ie, Arm B or Arm D, respectively).

Summary tables are based on data that are found to be "on-treatment"/ "treatment-emergent" for the oral or IV study drug as outlined in the below sections.

All safety data which is considered treatment-emergent will be summarized. Treatment-emergent is defined as safety data with an onset date on or after the date of first dose of study medication until the date of last dose of oral study drug plus 28 days or date of last IV dose plus 5 months (ie, 152 days), whichever is the latest date.

Descriptive statistics of safety will be presented using the NCI CTCAE v5.0. All AEs, drug-related adverse events, serious adverse events (SAEs) and drug-related SAEs will be tabulated using the worst grade per NCI CTCAE v5.0 by system organ class and preferred term. On-study lab parameters including hematology, coagulation, chemistry, liver function, thyroid, adrenal and renal function will be summarized using worse grade by NCI CTCAE v5.0.

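### The protocol's stop on SAE collection at subsequent anticancer therapy has no minimum period and contradicts the 28-day and 5-month reporting windows elsewhere in the protocol and in the COMBO SAP

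*Protocol*

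**What the plan says.** **The stop rule.** Protocol 3.1.6 (Post-treatment Follow-up Phase): "If a patient begins subsequent anticancer therapy, the sponsor will terminate collection of SAEs, with the exception of the AESIs of MDS and AML". Section 7.5.4.1 repeats the sentence. Table 5 footnote v has nearly the same wording: "If a patient discontinues from treatment and begins a subsequent anticancer therapy, the sponsor will terminate collection of SAEs". It makes the same MDS/AML exception. None of the three gives a minimum time since the last dose or an exception for drug-related or immune-mediated events.

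**The reporting windows.**
- Section 3.1.6 opens with: "All patients will be followed for at least 5 months after the last IV dose of study treatment".
- Section 7.5.4.1 says: "patients will be monitored for all AEs/SAEs/AESIs during study participation and until 28 days after the last dose of oral study drug". It adds the 5-month IV window and takes the later of the two.
- Section 7.4.6 keeps SAEs related or possibly related to the IV drug in scope until the 5-month visit (SFU2).
- Section 8.2 makes any fatal event through 28 days after the last dose an SAE.
- Section 8.7, on SAEs and AESIs, gives the same 28-day oral window and then states: "5 months after receiving the last dose of IV study drug, whichever is later, whether or not related to study drug, must be reported immediately".
- Section 8.10: "All SAEs and AESIs, regardless of relationship to study drug, must be reported to the sponsor/ SAE designee within 24 hours", over the same 28-day and 5-month periods.

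None of these windows carries an exception for subsequent therapy.

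**The analysis.** COMBO SAP Section 11 ends treatment-emergent data at a 28-day oral limit and, for the IV drug, at: "date of last IV dose plus 5 months (ie, 152 days), whichever is the latest date". Section 11.1 repeats this for adverse events. Neither section mentions subsequent therapy.

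**The concern.** Progression normally ends study drug (Protocol 3.1.3), so next-line therapy can begin while the safety windows are still open. At that moment one set of sections tells the sponsor to stop collecting SAEs and another requires them. The protocol set a 5-month window for IV-related events, and the stop rule can remove most of it for a patient who switches early.

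The analysis would not show this. The COMBO SAP applies one nominal window to everyone, but actual SAE ascertainment could end at the switch for some patients and run to day 152 for others. The switch is a post-randomization event whose timing may differ by arm. Serious-TEAE and immune-mediated AE percentages would then compare unequal observation periods without saying so. Sites that resolve the conflict differently would add inconsistency of their own.

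**Working it through.** There is no sample size or power figure at issue. The check compares the rules and then asks how much of the window could fall after the stop.

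**1. The SAP's window length.** 5 × 365.25 / 12 = 152.2 days, which agrees with the SAP's 152.

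**2. The rules side by side, for a patient who starts new therapy inside the window.**

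| Event | Stop sentence (3.1.6, Table 5 note v, 7.5.4.1) | Other sections |
|---|---|---|
| SAE within 28 days of last dose | Not collected | Required (8.7, 8.10) |
| Death within 28 days of last dose | Not collected as an SAE | Must be an SAE (8.2) |
| IV-related SAE, 28 days to 5 months | Not collected | Required (7.4.6, 8.7, 8.10) |
| Non-serious IV-related AE, 28 days to 5 months | Not mentioned | Recorded (8.7) |
| MDS or AML | Collected | Required |

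The first three rows are direct conflicts. Because the stop sentence names only SAEs, a literal reading keeps a non-serious IV-related event at month 3 and drops a serious one.

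**3. A second conflict, within Section 8.** For SAEs unrelated to study drug between 28 days and 5 months, the 24-hour reporting paragraph of 8.7 and the opening of 8.10 require reporting regardless of causality. The earlier paragraphs of 8.7 and a later sentence of 8.10 limit reporting after 28 days to related events. IV-related SAEs are required on either reading, so the conflict in step 2 does not depend on this one.

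**4. Share of the window after the stop.** Let g be the days from last dose to new therapy, with both drugs last given on the same day. The documents do not give g, so the values below are assumptions.

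IV window after the stop = (152 − g) / 152. 28-day window after the stop = max(0, 28 − g) / 28.

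| g (days) | IV window after stop | 28-day window after stop |
|---|---|---|
| 14 | 138/152 = 90.8% | 14/28 = 50% |
| 28 | 124/152 = 81.6% | 0% |
| 56 | 96/152 = 63.2% | 0% |
| 84 | 68/152 = 44.7% | 0% |
| 112 | 40/152 = 26.3% | 0% |

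The 28-day window is touched only by switches within 28 days. The 5-month IV window is the main exposure.

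**The case against.** The strongest reply is that the sentence was meant only to close the open-ended late tail. In Table 5 footnote v and in 7.5.4.1 it comes after the text saying that, once the windows have passed, only related SAEs and MDS/AML are reported. Removing SAEs from that list leaves exactly MDS and AML, the stated exception. In 3.1.6 it follows the paragraph on long-term follow-up. The odd literal result, serious events dropped and non-serious ones kept, also suggests that the literal reading was not intended. Footnote v and 7.5.4.1 both refer to Section 8 for the details, and AE monitoring is scheduled at SFU1 and SFU2 for all patients. A site following those sections would still report.

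This stands as a plausible account of intent, and it means that loss of data is not established. It does not remove the contradiction: the sentence is unrestricted in all three places, and nothing limits it to the post-window period.

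A reader might go further and infer that immune-related SAEs are certainly missing, or that the A versus B comparison is biased in a known direction. The documents support neither. Site practice is not described. Arm B receives IV placebo and so has no nivolumab toxicity to lose, while the planning medians (28 versus 20 months) would suggest earlier progression there, so no net direction follows. Those medians also cannot size the problem. They describe progression or death, deaths lead to no next therapy, and treatment may continue past progression. What matters is the share of patients starting new therapy within the window, which is not given.

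Timing is a fair practical objection. Protocol 9.2.2 expected randomization to close in the third quarter of 2020. End of September 2020 plus one 28-day cycle, 24 months of combination treatment and 5 months is about the end of March 2023, before Amendment 5 (16 June 2023). COMBO SAP 7.1 also expects all patients to be off treatment at cut-off. On that expected timetable, new wording would collect little prospectively.

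**Conclusion.** The point holds as a contradiction between reporting rules, with possible but unquantified loss of serious events. Three places in the protocol end SAE collection at subsequent therapy with no time floor. Sections 7.4.6, 8.2, 8.7 and 8.10 require at least IV-related SAEs to 5 months, and deaths to 28 days, without that exception. The COMBO SAP analyses the full window as though collection were complete.

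The percentages in the working are shares of one patient's IV window under assumed switch times. They are not rates of lost SAEs and say nothing about how many patients switch. Loss occurs only where the stop sentence was applied literally inside a window. The passages need to be reconciled, and the COMBO report needs to be open about the possible truncation.

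**What to change.** **Protocol.** State in 3.1.6, Table 5 footnote v and 7.5.4.1 that the stop at subsequent therapy applies only after the Section 8 reporting windows. It would then not end SAE collection within 28 days of the last dose, nor collection of IV-related SAEs up to 5 months after the last IV dose. Repeat this in 8.7 and 8.10. In the same change, settle whether unrelated SAEs between 28 days and 5 months are reportable, since 8.7 and 8.10 each say both.

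**COMBO SAP.** Keep the treatment-emergent window as defined. Flag events with onset after the start of subsequent therapy, and add a supportive summary of serious TEAEs and immune-mediated AEs censored at that start. Do not cut events unrelated to the IV drug from the main window, because that would remove rucaparib-related SAEs within 28 days.

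**If the windows have already closed.** State in the report that SAE collection may have stopped at the switch, and give by arm the number of patients who started new therapy within the window.

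**Cost.** Protocol wording, a flag and one supportive summary. SFU1 and SFU2 are already scheduled. The downside is that some SAEs due to next-line therapy will be reported and need a relatedness call.
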